Open Label Study to evaluate Efficacy and Safety of Short-Term, Adjunctive Adrenocorticotropic Hormone (ACTH) Gel Therapy in Rheumatoid Arthritis.

Protocol Version: 0.01 / 04/Apr/2022

Clinical Trials.gov: NCT02030028

Principal Investigator: [name]

University of Pittsburgh

Division of Rheumatology and Clinical Immunology

[name]

[name]

[name]

[contact]

Trial design: open label for 12 weeks

Dose/Route/Regimen: ACTHAR gel 80u subcutaneously twice weekly

Target population: 20 refractory adult Rheumatoid arthritis patients

Glossary of terms in protocol:

RA = rheumatoid arthritis

CDAI = clinical disease activity index

DAS = disease activity score

ESR = Erythrocyte sedimentation rate

CRP = C-reactive protein

A. Background and Rationale:

Adrenocorticotrophic hormone (ACTH) gel (repository corticotropin injection) (ACTHAR) is a long-acting full sequence ACTH that includes other pro-opiomelanocortin peptides (1-6). ACTH is thought to have anti-inflammatory prospects as well as immunomodulatory effects mediated through melanocortin receptors (2). ACTH gel is FDA approved for several immune-mediated disorders including rheumatoid arthritis (RA), multiple sclerosis, systemic lupus erythematosus, polymyositis, nephrotic syndrome, and infantile spasm syndromes (1-6).

RA is a chronic systemic autoimmune inflammatory arthropathy of unknown etiology (7). The worldwide prevalence is approximately 1% of adults of all races. Disease onset occurs most often between the ages of 20 and 60 years, with peak occurrences at 50 to 60 years. The prevalence of RA varies with sex and age, and is higher in women than in men. Affected subjects experience considerable morbidity, including symptoms such as joint stiffness, pain and swelling, rapid loss of function, joint destruction, permanent deformity as well as a reduced life expectancy.

The treatment of RA has seen a dramatic paradigm shift over the past decade with the introduction of biologic response modifiers (5 that inhibit tumor necrosis factor, 1 inhibitor of interleukin-1, 1 that blocks interleukin-6, 1 that inhibits B-cells, and 1 that blocks co-stimulatory pathways), plus most recently an oral agent that blocks Janus

Kinase pathways. In addition, treatment with standard oral medications such as triple oral disease modifying drugs (DMARDs) also are effective options (7). Despite these advances, a large percentage of our patients require daily therapy with oral prednisone and/or don't respond to these current therapies. Thus, safe new therapies are still needed for this common immune-mediated inflammatory disease.

B. Hypothesis and Specific Aims:

Hypothesis: Patients with RA, who are receiving stable doses of background medications will have an improvement in disease activity (as measured by CDAI) when treated with 12 weeks of subcutaneous ACTHAR.

Specific aim 1: To determine the efficacy and safety of ACTH gel in refractory RA patients.

Specific aim 2: To determine the potential mechanisms of action of ACTH gel, pending review of efficacy data.

C. STUDY Design:

The proposed trial design would be open-label with a subcutaneous dose of ACTHAR 80 units, twice a week, for 12 weeks. The entry criteria would be:

1. RA diagnosis by ACR criteria
2. Active disease (CDAI > 10) (8, 9, 10)
3. Have received at least one biologic agent for at least 6 months

4. May or may not be receiving oral daily steroids (less than or equal to 20 mg/day) of prednisone equivalent
5. No current active infections requiring antibiotics
6. Patients must be on stable doses of RA therapies (e.g., methotrexate or other RA therapies for at least 4 weeks prior to baseline visit)

Table 1. Proposed Study Visits and Study Activities

	Screening	Baseline	2wk	4wk	8wk	12wk	16wk
Informed Consent	X						
Dispense medication		X		X	X	X	
Clinical Labs*	X		X	X	X	X	X
AE Monitoring			X	X	X	X	X
Efficacy assessments		X	X	X	X	X	X
Research Labs (PBMC's, serum, plasma, RNA)		X	X	X	X	X	X

*CBC, glucose, creatinine, ESR, CRP, ALT

Patient population and estimated sample size: Patients will be recruited from UPMC Rheumatology Outpatient Clinics. A pilot study of 20 patients will provide initial information on efficacy of this agent in refractory RA patients. For the year ending in Spring 2012, we had over 4,000 unique, active RA patients in our outpatient clinics. We have 35 Rheumatologists who practice at UPMC in Western, PA.

Primary end-points:

1. Changes in CDAI at week-12 (9); we propose a 20% improvement after 12 week of therapy compared to baseline as a positive response.

Secondary end points:

1. Changes in DAS28-CRP (9, 10)
2. Changes in acute phase reactants (ESR, CRP)
3. Changes in fatigue, as measured by FACIT (11).

D. Data Analysis:

We will determine the frequency of subjects who have at least a 20% improvement in CDAI from baseline to week 12 visit. We will document the frequency and events of adverse event. For secondary endpoints we will also determine frequency of subjects what have at least 20% improvement in DAS28-CRP, fatigue, ESR and CRP from baseline to week 12.

E. Data captured and Database:

The Division of Rheumatology and Clinical Immunology has experience spanning four decades in the development, maintenance and refinement of disease-specific databases of longitudinal cohorts of patients with rheumatic diseases. In the past few years we have developed a web-based database that we plan to use for this investigator-initiated trial. The key characteristics of the Rheumatic Disease Musculoskeletal System (RDMS) are: **1)** the ability for longitudinal data collection and database management of data

from multiple clinic visits; **2)** the ability to use multiple methods of data entry (e.g., web-based, tablet-based, or manual from hard copy) that permit secure data collection at various UPMC clinics, other institutions or Academic Medical Centers; **3)** data capture and synthesis in real-time has the ability to provide immediate feed-back to clinic staff and patients with regards to the data collected and trends over time; **4)** flexibility to meet the needs of diverse researchers and their research questions through a modular design allowing for customization of data collection specific to individual study questions; **5)** adaptability for future research studies through the addition of new forms or disease-specific modules; **6)** easy accessibility of data for analysis by research team members with limited programming and statistical training such as coordinators, fellows and faculty; **7)** capability for automated downloading and database integration of discrete well-defined clinical data, such as medication data, laboratory data and imaging data, from other electronic UPMC systems (e.g., EPIC electronic medical record system, Medical Archival Record System (MARS)); **8)** patient data is separated into different data modules (e.g., Health Insurance Portability and Accountability Act (HIPAA) identifiers, demographic information, generic connective tissue disease data and disease-specific data) with restricted user access and linkage between the HIPAA information and other data based on a unique 8-digit subject ID number; **9)** a set of common definitions for terms and data collection forms used in the database and the establishment of a committee to oversee the common definitions and forms; and **10)** a research biospecimen and sample tracking system module.

F. Exploratory future objectives:

Once the clinical trial is completed we will consider what mechanistic studies to pursue.

We plan to collect appropriate samples and store in -80% freezer in one of the Rheumatology Division's freezers.

G. Proposed time line:

Estimated time line (including IRB approval, study initiation, enrollment, study completion and submission of publication):

2 year trial

- 6-month start-up (develop forms; IRB submission)
- 18-month recruitment and follow-up

H. References:

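### Table 1 dispenses study drug at week 12, when the stated 12-week course is already complete, and nothing in the protocol explains why

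*Combined protocol and SAP*

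**What the plan says.** Two passages state the length of treatment directly. Section C reads: "The proposed trial design would be open-label with a subcutaneous dose of ACTHAR 80 units, twice a week, for 12 weeks". The hypothesis in Section B refers to patients "when treated with 12 weeks of subcutaneous ACTHAR".

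Two more are consistent with that. The front-page summary has "Trial design: open label for 12 weeks", and the primary endpoint reads "we propose a 20% improvement after 12 week of therapy compared to baseline as a positive response".

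The dispensing row of Table 1 reads "Dispense medication X X X X". Its four marks stand under Baseline, 4wk, 8wk and 12wk. Screening, 2wk and 16wk are blank.

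The only footnote to Table 1 lists the clinical laboratory tests. The protocol mentions no taper, extension, drug return or treatment after week 12, and it does not state the purpose of the week 16 visit. It gives no supply quantities and no visit windows.

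**The concern.** A course that lasts 12 weeks from Baseline is over by the week 12 visit, so drug dispensed at that visit has no stated use. Table 1 is the schedule that site staff would work from. Followed as written, it has them hand out study drug at the end of the stated course.

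Whether that drug is used changes total exposure. It also changes what the week 16 visit represents: an assessment on continuing drug, or one four weeks past the end of treatment. Table 1 schedules adverse event monitoring, clinical labs, efficacy assessments and research samples at week 16. Safety is part of Aim 1 ("To determine the efficacy and safety of ACTH gel in refractory RA patients"), and Section D does not limit the adverse event summary to week 12, so week 16 events would enter it. Mechanism is Aim 2, and the stored samples are meant to serve it.

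**Working it through.** **Inputs.** Twice-weekly dosing for 12 weeks (Section C); dispensing at Baseline and weeks 4, 8 and 12, and the visit schedule (Table 1); 20 patients (front page and Section C). Assumptions: first dose at the Baseline visit, visits on nominal days, full attendance.

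**1. Position of the marks.** In the text of Table 1 the header and the dispensing row each split into 8 cells, as do the other rows. Matched cell by cell, the dispensing marks fall at Baseline, 4wk, 8wk and 12wk, and the marks in the other rows fall at plausible visits.

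**2. Size of the stated course.** 12 weeks × 2 per week = 24 injections.

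**3. When the course ends.** Take the first dose as day 0.
- Doses on days 0 and 3 of each week: last dose on day 77 + 3 = 80.
- Doses on days 0 and 4 of each week: last dose on day 77 + 4 = 81.
- Week 12 visit: 12 × 7 = day 84.

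Both patterns finish before the visit.

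**4. Injections due after each dispensing mark.**

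| Interval | Injections of the stated course |
|---|---|
| Weeks 0–4 | 8 |
| Weeks 4–8 | 8 |
| Weeks 8–12 | 8 |
| Weeks 12–16 | 0 |
| Total | 24 |

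Table 1 has no dispensing mark between weeks 8 and 12. The first three dispensings must therefore supply all 24 injections, whatever quantity is given each time.

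**5. Could timing slippage explain the mark?** Suppose the first dose is late or the visit is early by up to 7 days (an assumption). The injections remaining on or after the week 12 visit are:
- 0 for a shift of 0–2 days
- 0 or 1 for 3 days, depending on spacing
- 1 for 4–6 days
- 2 for 7 days

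If both slip by 7 days, the visit falls 84 − 14 = 70 days after the first dose. Four injections then remain (days 70, 73, 77 and 80, or 70, 74, 77 and 81).

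**6. Possible extra exposure, as an illustration only.** If the week 12 supply lasted four weeks, it would hold 4 × 2 = 8 injections. The total per patient would lie between 24 (none used) and 32 (all used), and 8/24 = 33%, so 0% to 33% more. With no supply quantities stated, the documents set no upper limit.

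**7. Data whose label depends on the answer.**
- Adverse event monitoring ("AE Monitoring X X X X X"): 20 × 5 = 100 visits, of which 20 are at week 16 (20%).
- Research samples ("Research Labs (PBMC's, serum, plasma, RNA) X X X X X X"): 20 × 6 = 120 sets, of which 20 are at week 16 (17%).

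**The case against.** The other side accepts that the mark is there and unexplained, but argues that it matters little.

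- **The evidence is one mark in a table read from PDF.** Equal cell counts do not exclude a mark read into the wrong column. This stands as a caveat, although the plausible placement of every other row makes it unlikely. A look at the source table settles it.
- **The prose is not ambiguous, and dispensing is not dosing.** It is true that no passage states dosing after week 12. But dispensing a study drug implies a use, and the protocol supplies none.
- **Late or missed doses could explain the mark.** This stands in part. The limit of 2 of 24 holds only if the first dose is late or the visit early, not both; with both it is 4 of 24. Missed or held doses are not covered by either figure. A supply used only to complete 24 injections would not exceed the stated number. No passage describes such a use, however, and Table 1 marks the dispensing without condition.
- **No planned analysis turns on it.** Largely right. Section D analyses efficacy from baseline to week 12 and plans no exposure-adjusted adverse event rate. Aim 2 awaits the efficacy data, and Section F leaves the mechanistic work undecided. The percentages above count affected observations and do not measure bias. What remains is that adverse events and samples are collected at week 16 with no stated exposure status.
- **If the mark is a slip, correcting the cell is enough.** The duration text would then answer the on/off question by inference. An explicit label would be a low-cost clarification in that case.

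**Conclusion.** The concern holds. Table 1 and the stated treatment duration contradict each other, and nothing in the protocol reconciles them. Under nominal timing, 0 of 24 injections remain at the week 12 visit. A shift of up to 7 days in either the first dose or the visit leaves at most 2.

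The consequence is confined to total exposure and to the reading of week 16 data. That covers one fifth of the adverse event visits and about one sixth of the research sample sets, assuming 20 patients with full attendance. The week 12 efficacy results are not affected, provided the week 12 assessments are made before any use of that supply. The point should be fixed, but it does not threaten the primary analysis.

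**What to change.** Reconcile the dispensing row of Table 1 with the duration given in Section C and the hypothesis. The sponsor-investigator must decide which reflects the intended plan; this review takes no position. Then state in Table 1 and Section D whether weeks 12 to 16 are on or off drug, and identify adverse events and samples from that interval accordingly.

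**Cost.** If the mark is an error, one cell of Table 1 changes. If it is intended, the two direct statements of duration need revision, and the front-page summary and endpoint wording need checking. In either case add one label to Table 1 and one sentence to Section D. No new visits or data are required.

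### For efficacy, Section D plans only 20% responder frequencies, so the plan as written gives no estimate of the size of any change and no interval for the percentage.

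*Combined protocol and SAP*

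**What the plan says.** Section B states the hypothesis that patients "will have an improvement in disease activity (as measured by CDAI) when treated with 12 weeks of subcutaneous ACTHAR", with no threshold attached. The primary endpoint in Section C reads "Changes in CDAI at week-12 (9); we propose a 20% improvement after 12 week of therapy compared to baseline as a positive response". It therefore names a change and then defines a responder. The secondary endpoints in the same section have no threshold: "Changes in DAS28-CRP", changes in ESR and CRP, and "Changes in fatigue, as measured by FACIT".

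Section D is the whole analysis plan. For the primary endpoint it says "We will determine the frequency of subjects who have at least a 20% improvement in CDAI from baseline to week 12 visit". For DAS28-CRP, fatigue, ESR and CRP it again plans the frequency of patients improving by 20% or more. It also plans a description of adverse events. Neither Section D nor any other part of the document plans a mean or median change, a standard deviation, an interval or a confidence level.

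On purpose and size, Section C says "A pilot study of 20 patients will provide initial information on efficacy of this agent in refractory RA patients".

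**The concern.** A pilot that is meant to inform on efficacy needs no formal test, but it does need the size of the effect and its precision. Section D commits to neither. The two gaps differ in weight. A reader given x out of 20 can work out an interval unaided, but nobody can get back from a responder count to the size of the CDAI change. The secondary measures show the gap most clearly: each is listed purely as a change, and the only planned analysis is a cut at 20% that the endpoint list does not mention.

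There is also a matter of commitment. If the plan does not name the summary of change, that summary will be chosen, if at all, after open-label data have been seen.

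**Working it through.** **Inputs from the document.** Planned number of patients: 20 (Section C). Response: CDAI at week 12 at least 20% below baseline (Sections C and D). The document states no standard deviation, expected response rate, dropout rate or confidence level, so it has no precision figure to reproduce.

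**Assumptions.** Two-sided 95% intervals; all 20 patients evaluable unless stated; every baseline CDAI equal to 20 in the worked example.

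**1. Planned outputs against named endpoints.**

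| Measure | Named in Section C as | Planned in Section D |
|---|---|---|
| CDAI | change, with 20% as a positive response | frequency of ≥20% improvement |
| DAS28-CRP | change | frequency of ≥20% improvement |
| ESR, CRP | change | frequency of ≥20% improvement |
| Fatigue (FACIT) | change | frequency of ≥20% improvement |

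No row has a planned estimate of the size of change.

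**2. Precision of the responder proportion.** The exact (Clopper-Pearson) limits for x out of n are the 0.025 quantile of Beta(x, n − x + 1) and the 0.975 quantile of Beta(x + 1, n − x).

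- 8/20 (40%): 19.1% to 63.9%
- 10/20 (50%): 27.2% to 72.8%, about 46 percentage points wide
- 12/20 (60%): 36.1% to 80.9%
- 8/16 (50%, if only 16 are evaluable; assumed): 24.7% to 75.3%

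**3. Same count, different change.** With every baseline at 20, the cut is 0.20 × 20 = 4 points. The interval is mean ± t(0.975, 19) × SD/√20, and t(0.975, 19)/√20 = 0.468.

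- Case A: ten patients change by -4 and ten by +2. Responders 10/20. Mean = (10 × -4 + 10 × 2)/20 = -1.0. Each value lies 3 from the mean, so SD = √(20 × 9/19) = 3.08. Half-width = 0.468 × 3.08 = 1.44. The 95% CI is -2.4 to 0.4.
- Case B: ten patients change by -12 and ten by 0. Responders 10/20. Mean = -6.0. Each value lies 6 from the mean, so SD = √(20 × 36/19) = 6.16. Half-width = 0.468 × 6.16 = 2.88. The 95% CI is -8.9 to -3.1.

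Section D would report both cases as the same 10/20. In A the interval for the mean change includes zero; in B it does not.

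**4. What an added estimate would deliver.** The 95% half-width for the mean change is 0.47 SD of the change with 20 evaluable patients, and 0.53 SD with 16. With 20 patients that is 0.468 × 6 = 2.8 points if the SD is 6, and 0.468 × 10 = 4.7 points if it is 10. Both SDs are assumed.

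**The case against.** The strongest reply is that the 20% response is the endpoint. The primary endpoint is one sentence, its second clause can fairly be read as defining what the first means, and Section D analyses exactly that. This stands in part. A reader might infer that Section D contradicts the primary endpoint or puts a foreign one in its place. The text does not support that: the CDAI responder count belongs to the stated endpoint, and the analysis is incomplete rather than contrary. The reply does not reach the secondary measures, which have no threshold in Section C.

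Other objections narrow the point further:

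- *Nothing is lost.* Table 1 schedules efficacy assessments at baseline and at weeks 2, 4, 8, 12 and 16, so a change could still be estimated. True. The gap is in what the plan commits to, not in what the trial can produce.
- *The worked example is contrived.* It uses two-point distributions and a single baseline. It shows that a count does not determine the change; it does not show how far apart the two are likely to be here.
- *A relative cut is a different number of points for each patient.* That is true of any percentage criterion. It is not an error and gives no ground for removing the 20% response.
- *It is an uncontrolled pilot.* An interval or a mean change would be no easier to attribute to the drug than a percentage. This stands. It is a reason to state the limit, not to omit the estimate.

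A reader might also want a reference response rate to test against, or a figure for how many responders would appear with no drug effect. The document supplies no basis for either. Such figures would rest on assumed inputs and concern the missing control arm, which is a separate matter.

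**Conclusion.** The point holds as an incompleteness in Section D that should be corrected. For efficacy, the plan as written gives no estimate of the size of change on any measure and no interval for any percentage. That the count cannot stand in for the change follows from the definitions and needs no assumption. The illustration of its size (mean changes of -1.0 and -6.0 behind the same 10/20) assumes every baseline is 20. The 27% to 73% interval assumes 20 evaluable patients, a 50% response and 95% confidence.

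The point does not make the 20% response invalid, call for a hypothesis test or more patients, or mean that the trial could not estimate the change from the data it collects.

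**What to change.** In Section D:

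1. Add the mean within-patient change in CDAI from baseline to week 12 with a paired-t 95% CI, and a signed-rank analysis as a check.
2. Keep the 20% responder proportion and report it with an exact 95% CI and its denominator, saying how patients without a week-12 CDAI are counted.
3. For DAS28-CRP and FACIT, report the change with a 95% CI. For ESR and CRP, which are bounded at zero and may be skewed, report the median or log-ratio change with a 95% CI.
4. State that, without a control arm, neither the responder proportion nor the mean change separates drug effect from regression to the mean or open-label response.

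This takes a few sentences and a little more analysis of data already scheduled, with no new visits or patients. The downsides are that the headline percentage will carry a visibly wide interval, and that the two summaries may not agree.

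### Section D counts only patients whose CDAI improves by 20%, so worsening and the signed CDAI change go unreported, and a low to moderate response rate cannot be told from symmetric fluctuation.

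*Combined protocol and SAP*

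**What the plan says.** Section B states a directional hypothesis: patients on stable background treatment "will have an improvement in disease activity (as measured by CDAI) when treated with 12 weeks of subcutaneous ACTHAR". The primary end-point in Section C is a change, with a responder cut-off attached: "Changes in CDAI at week-12 (9); we propose a 20% improvement after 12 week of therapy compared to baseline as a positive response".

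Section D carries only the cut-off forward: "We will determine the frequency of subjects who have at least a 20% improvement in CDAI from baseline to week 12 visit". The secondary measures are treated the same way: "we will also determine frequency of subjects what have at least 20% improvement in DAS28-CRP, fatigue, ESR and CRP from baseline to week 12". The other planned output is the frequency of adverse events. Neither section defines or counts worsening. Neither plans a mean or median change, an interval, a test or a reference response rate.

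The trial is a single open-label arm, described thus: "A pilot study of 20 patients will provide initial information on efficacy of this agent in refractory RA patients". Entry requires CDAI above 10. Table 1 schedules efficacy assessments at baseline and at weeks 2, 4, 8, 12 and 16, but none at screening.

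**The concern.** A count of 20% falls keeps one tail of the distribution of change. A patient whose CDAI rises by half is tabulated with one who has not moved. CDAI varies from visit to visit, so some patients will cross a 20% cut-off in each direction even if the drug does nothing. A control arm would show how many. Here there is none, and no external rate is named for comparison.

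The hypothesis concerns net improvement, and the planned output does not measure it. A modest response rate from 20 patients could be read as a signal of efficacy when as many patients moved the other way. The data that would show this are already scheduled.

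**Working it through.** **No figure to reproduce.** The documents give no alpha, power, null response rate, CDAI SD or dropout, and 20 patients has no calculation behind it. Everything on variability below is an assumption, shown as a range.

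**Mirror cut-off.** Let B be baseline and W week 12. Improved is W ≤ 0.80B. Since 1/0.80 = 1.25, the mirror event is W ≥ 1.25B. Exchanging B and W turns one into the other, so with no true change, similar error at both visits and no selection, the two have equal expected counts.

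**One response rate, different pictures.** Section D would report 6/20 = 30% in each case. Two-sided exact sign tests:
- 6 improved, 0 worsened: p = 2 × 0.5^6 = 0.031; net +6/20 = +30 points.
- 6 improved, 2 worsened: p = 2 × (28 + 8 + 1)/256 = 0.29; net +20 points.
- 6 improved, 6 worsened: p = 1.0; net 0.

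**Symmetric noise only.** Assume independent error of SD s on log CDAI at each visit and no true change. Then P(improved) = Φ(ln 0.8/(s√2)) = P(worsened).
- s = 0.10: 5.7% each way, about 1 of 20.
- s = 0.20: 21.5% each way.
- s = 0.30: Φ(−0.223/0.424) = 29.9% each way, about 6 of 20.

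With s = 0.10, reaching the same 29.9% needs a true geometric-mean ratio of exp(−0.223 + 0.526 × 0.141) = 0.862, and then only 0.4% worsen. The response rate is identical in these two cases; the worsened count separates them.

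**Adding the entry rule.** Assume normally distributed true CDAI, independent normal visit error, no true change, and the entry reading also serving as baseline (Table 1 lists no screening efficacy assessment). Each scenario was simulated with 2,000,000 patients, keeping those with baseline above 10. Means and SDs are before the entry rule. The share removed is worsened divided by improved.

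| Mean (SD) | Visit SD | Improved | Worsened | Net, points | Share removed |
|---|---|---|---|---|---|
| 12 (5) | 2 | 17.2% | 8.3% | 8.9 | 48% |
| 12 (5) | 5 | 43.2% | 18.5% | 24.7 | 43% |
| 15 (7) | 2 | 11.8% | 7.0% | 4.8 | 59% |
| 15 (7) | 5 | 35.3% | 20.4% | 14.9 | 58% |
| 18 (7) | 2 | 9.1% | 6.2% | 2.9 | 68% |
| 18 (7) | 5 | 31.0% | 21.2% | 9.8 | 68% |
| 25 (10) | 2 | 4.7% | 3.5% | 1.2 | 74% |
| 25 (10) | 5 | 22.8% | 18.6% | 4.2 | 82% |

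So 5% to 43% respond with no effect, and 1 to 25 points remain after netting. A harsher log-scale model (population median 10, s = 0.40) leaves about 31 points.

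**Would a rule of improved exceeding worsened work?** Put the no-effect rates into an exact trinomial with n = 20 and sum over all outcomes with more improved than worsened. For mean 18 and visit SD 2 to 5 the probability is 0.51, 0.59, 0.64 and 0.68. For mean 25 it is 0.40, 0.48, 0.52 and 0.55. For mean 12 it reaches 0.91. The entry rule also shifts the null of the sign test: at mean 18 and visit SD 5, improvers are 31.0/(31.0 + 21.2) = 59% of those who move, not 50%. The test can therefore only be descriptive.

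**The case against.** The strongest reply is that this is a pilot meant to give initial information, with no success criterion, and that a responder count is a legitimate summary. Wording the endpoint as a change leaves room for a signed analysis. If visit error is small, noise yields about 1 responder in 20. Symmetric noise alone cannot lift the expected rate above 50%, so 15 or more of 20 (exact lower 95% limit above 50%) would be hard to explain by it. All of this stands. It confines the problem to low and moderate rates, but does not supply the missing analysis.

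Three stronger readings are tempting, and the documents do not support them:
- That worseners are the only internal gauge of fluctuation. Table 1 provides repeated readings, which would show, for example, whether a week-12 response was already present at week 8.
- That the plan hides deterioration. CDAI would be recorded at each post-baseline visit, and adverse events are monitored from week 2 to week 16 and reported. What is missing is a summary of CDAI worsening, not the observation of it.
- That equal counts would show the drug does nothing. Six against six in 20 patients is compatible with a real effect.

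On choice of method, a signed mean or median change with an interval shows net direction without a new cut-off, but not how many patients deteriorated. The two belong together.

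**Conclusion.** The gap is real but limited. Section D does not analyse the signed change that Section C names, and it merges worsened with unchanged patients. With no control arm or reference rate, a response rate around 6 of 20 therefore cannot separate fluctuation from net improvement.

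The size rests wholly on assumed variability: 5% to 43% spurious response in the scenarios tabulated, of which counting worseners removes roughly 40% to 80%. A reader might infer that netting cleans up the result, or that improvers outnumbering worseners supports the hypothesis. Neither follows. Regression to the mean from the entry rule and open-label expectation both survive netting, and a drug with no effect would satisfy such a rule in about 40% to 68% of trials at means 18 and 25, and more often at lower means. Nor is the responder rate worthless at every level; a high rate remains informative against symmetric noise. This is a cheap improvement, not a defect that invalidates the trial.

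**What to change.** Keep the 20% responder rate as the headline CDAI result and add to Section D:

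- Counts, out of all treated patients, of improved (week 12 at most 0.80 × baseline), worsened (at least 1.25 × baseline), neither, and no week-12 CDAI. Show the last group separately, so that a patient who deteriorates and leaves early is not placed in neither.
- An exact sign test of improved against worsened, labelled descriptive.
- The mean or median signed change in CDAI from baseline to week 12, with a 95% interval.
- A sentence stating that regression to the mean from the CDAI entry rule and open-label expectation are not removed by these summaries.

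Do not add a rule that the hypothesis is supported when improved exceed worsened.

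The cost is one extra table and a few sentences, using assessments already in Table 1. No visit or procedure changes. The downside is that the result may look less favourable than the response rate alone.

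### The 20% improvement rule is applied to FACIT fatigue without stating the scale, range or direction; if higher scores mean less fatigue, the hurdle rises with baseline and the top sixth of the range cannot respond

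*Combined protocol and SAP*

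**What the plan says.** Section C lists as a secondary end point "Changes in fatigue, as measured by FACIT (11"). Section D gives the only fatigue analysis, the "frequency of subjects what have at least 20% improvement in DAS28-CRP, fatigue, ESR and CRP from baseline to week 12".

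The 20% cut comes from the primary endpoint, change in CDAI, for which Section C says "we propose a 20% improvement after 12 week of therapy compared to baseline as a positive response". CDAI is a higher-is-worse index in this plan, as the entry criterion shows: "Active disease (CDAI > 10) (8, 9, 10").

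The plan does not say which FACIT scale is used, what its range is, whether a high score is good or bad, or how the 20% is calculated for fatigue. FACIT is absent from the glossary, and the title of reference 11 describes a measurement system, not one scale. None of the six entry criteria limits baseline fatigue, and no expected baseline score is given.

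**The concern.** A percentage of baseline behaves sensibly when zero is the good end of the scale: the worse the patient, the larger the change required, and everyone above zero has room to reach it. If zero is the bad end, both properties fail. The most fatigued patients need the smallest change, and those who start near the top have too little scale left to gain 20%.

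Section D carries the CDAI rule over to fatigue without saying which case applies. If FACIT is scored so that higher is better, the fatigue response rate mixes real change with where each patient started. The trial has one open-label arm, so no comparison group would show the distortion. With 20 patients, each one reclassified moves the rate by 1/20 = 5 percentage points.

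**Working it through.** The plan gives no figure to reproduce for this endpoint, so the check is direct arithmetic on the stated rule.

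**Inputs from the documents:** a 20% improvement from baseline to week 12 (Section D); FACIT as the instrument (Section C); 20 patients, single arm (Section C); no baseline fatigue restriction (Section C).

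**Assumptions, not in the documents:** the score runs from 0 to M; higher means less fatigue; the 20% is relative to the patient's own baseline b. M is varied over 40, 52, 100 and 160.

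**Step 1: gain required.** Required gain = 0.20 × b. This gives 1 point at b = 5, 2 at 10, 3 at 15, 4 at 20, 6 at 30 and 8 at 40. At b = 0 the percentage is undefined.

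**Step 2: ceiling.** Response requires 1.2 × b ≤ M, so it is impossible when b > M/1.2.

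| Assumed M | M/1.2 |
|---|---|
| 40 | 33.3 |
| 52 | 43.3 |
| 100 | 83.3 |
| 160 | 133.3 |

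The excluded share of the range is 1 − 1/1.2 = 16.7%, one sixth, whatever M is. With M = 52 and whole-number scores, exclusion starts at 44: the need is 0.20 × 44 = 8.8 points and only 52 − 44 = 8 are available.

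**Step 3: same answers scored in the opposite direction (M = 52).** The score becomes 52 − b, improvement is a fall, and the required fall is 0.20 × (52 − b).

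| Baseline b (higher = less fatigue) | Gain needed | Fall needed if reversed |
|---|---|---|
| 10 | 2 | 8.4 |
| 20 | 4 | 6.4 |
| 30 | 6 | 4.4 |
| 40 | 8 | 2.4 |

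With reversed scoring, no patient with a score above 0 is barred from responding.

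**Step 4: one change, two classifications.** Take a 5-point improvement with M = 52.

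- From b = 20: 5/20 = 25% (responder); reversed, 5/32 = 15.6% (non-responder).
- From b = 30: 5/30 = 16.7% (non-responder); reversed, 5/22 = 22.7% (responder).

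Identical answers and an identical change give opposite results. A fixed-point change would classify these patients the same way in either direction.

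**The case against.** The strongest objection is that the range and direction come from outside the documents. The plan says only FACIT, and the cited reference cannot be consulted here. If higher meant more fatigue, the ordering would reverse and the ceiling would vanish. This stands: both are assumptions, and the result is conditional on them. It does not remove the point, because the plan leaves the direction open and the classification changes with it.

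The relative formula is also inferred. The comparison with baseline is written out as the definition of a positive response only for CDAI. For fatigue it is the natural reading of a 20% improvement from baseline, but no formula is given. This too stands as a limit.

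A reader might infer that, in this trial, the most fatigued patients will respond with about 2 points and the least fatigued cannot respond at all. The documents do not support that. About 2 points needs a baseline near 10 (baselines of 5 to 15 give 1 to 3 points), and exclusion needs a baseline of 44 or more if M = 52. No baseline distribution is given, so the number of patients in either zone is unknown and could be none.

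A reader might also infer that response has nothing to do with how much fatigue changed. That is wrong: at any given baseline, response depends entirely on the change. Only the threshold moves with baseline and scoring direction.

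Finally, the stakes are limited. The plan describes the study thus: "A pilot study of 20 patients will provide initial information on efficacy of this agent in refractory RA patients". Fatigue response is one of several secondary summaries, with no test or decision rule attached. That bears on priority. It is not a reason to leave the rule as it is, since no other fatigue analysis is planned.

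**Conclusion.** The concern holds in conditional form. The documents establish that fatigue is analysed only by a 20% improvement cut shared with CDAI, with the score, range, direction and calculation left undefined. Arithmetic establishes that, on any zero-based scale where higher is better, this rule asks least of the most fatigued and makes response impossible in the top sixth of the range.

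The point figures rest on three assumptions: a zero-based scale, higher meaning less fatigue, and a change relative to baseline. Those for individual baselines with a ceiling of 43.3 also assume M = 52. Classification therefore depends on scoring direction and baseline as well as on the change. The effect on the reported fatigue response rate cannot be sized without a baseline distribution. The point is confined to the fatigue endpoint and is worth correcting; it does not touch the primary CDAI analysis.

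**What to change.** In Section D:

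- Name the FACIT scale used, its range and its direction.
- Remove fatigue from the list of measures judged by the 20% rule.
- Report the mean change in the fatigue score from baseline to week 12 with a confidence interval. This matches the endpoint as listed in Section C, which is a change and not a response.
- If a responder frequency is kept, define it as a fixed number of points, the same for every patient, taken from the instrument's guidance and set before the data are read. The documents give no value for this cut.

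The cost is a short edit to Section D and no new data. There are two downsides. Fatigue would no longer share the 20% cut used for the other endpoints. A fixed cut of k points would also still exclude baselines above M − k: purely as an illustration, k = 4 with M = 52 excludes 49 to 52, a smaller zone than the 44 to 52 excluded by the 20% rule. The mean change uses no cut and so excludes no one by baseline score.
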